3. ELIGIBILITY CRITERIA

3.1. Inclusion criteria

Patients will be eligible for the study if they satisfy all of the following criteria:

1. Presence of a pelvic/abdominal lesion with suspicion of a primary malignancy, disease recurrence, or disease progression
 - a. new diagnosis of a presumed gynecologic tumor
 - b. suspected recurrence or progression of a known gynecologic malignancy
 - c. pelvic/abdominal spread or recurrence of a non-gynecologic tumor (tumor itself or metastasis)
 - d. pelvic/abdominal spread of a tumor of unknown origin.
2. Age ≥ 18 years
3. Eastern Cooperative Oncology Group Performance Status (ECOG PS) grade < 3
4. Not pregnant
5. Signed informed consent form

3.2. Exclusion criteria

Patients will be excluded from the study for the following reasons:

1. Considered by the investigator to be unsuitable for any treatment
2. Early stage disease
3. Age < 18 years

4. STUDY DESCRIPTION

Patients referred to the Gynecologic Oncology Centre with a new or recurrent progressive abdominal/pelvic tumor will be clinically examined. The standard of care imaging method will be performed as part of preoperative work-up, including expert transvaginal US (TVS), transrectal and transabdominal US (TAS) or computed tomography (CT), magnetic resonance imaging (MRI), or positron emission tomography (PET)/CT scan.

Eligible women meeting all the inclusion criteria will be identified by a clinician. They will be provided with the “Informed consent” and “Information for patients” documents, and the objectives and the course of the study will be discussed with them. After obtaining written consent, patients will be registered into the database using the REDCap (Research Electronic Data Capture, www.project-redcap.org) electronic data capture tool. This is a secure, web-based application with controlled access designed to support data capture for research studies, hosted at MD Anderson. Basic clinical data about patients will be compiled using the *Clinical data form*. The REDCap service complies with GDPR/data regulations.

Before the procedure, the patient’s risk factors for bleeding (e.g. history of bleeding, and current use of antiplatelet or anticoagulant agents) will be carefully evaluated. In patients with any risk factors, their platelet (PLT) count and coagulation status will be tested and controlled by the physician performing TCB. In patients with thrombocytopenia or a prolonged prothrombin time and activated thromboplastin time, preventive measures should be discussed with a hemostasis specialist. PLT count $> 50 \times 10^9/L$ and an international normalized ratio (INR) > 1.5 are considered safe [12, 13]. In patients using low molecular weight heparin (LMWH), TCB should be not be performed within 12 h after the loading dose, or within 24 h after a therapeutic dose. In patients using vitamin K antagonists, TCB should be performed at least 5 days after last tablet [14]. In patients using new anticoagulant drugs (NOAC), it is only necessary to skip a single dose before and after TCB. Patients who are unable to undergo TCB due to hematologic complications will be excluded from the trial.

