4.1. DESCRIPTION OF TCB

Because of the very low rate of complications associated with pelvic TCB, it is considered a low-risk procedure and, as such, can be performed in an outpatient basis. It does not require any special preparation of the patient, laboratory tests (except in patients with high risk of bleeding), fasting, or general anesthesia, and it involves a short procedure time. Anxious, risky patients and those who are unable to tolerate US should be offered conscious sedation or general anesthesia in an inpatient setting. Patients referred for surgical treatment according to clinical staging will undergo TCB just

before main surgery under anesthesia. For the other patients, TCB should be done as soon as possible after US, with a maximum interval of 1 week.

The physician who performs TCB according to US will choose the best suitable approach, such as vaginal/ transrectal or abdominal/percutaneous; in some cases, both routes may be used. If the lesion is accessible by two different approaches (transvaginal and percutaneous), the preferred approach is transvaginal because the needle is easier to control, the needle tip can be continuously monitored easily, the higher resolution of the endovaginal probe, and the gynecologist usually has greater experience of this approach. All biopsies will be performed by physicians with training in performing gynecologic US and TCB.

Antibiotic prophylaxis is recommended after transrectal biopsy if the needle passes through the rectal wall into the peritoneal cavity and in immunocompromised patients [15, 16]. The main principles of clean contaminated procedures must be followed when performing invasive procedures to minimize the risk of infection.

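### The INR limit for biopsy is printed the wrong way round: values above 1.5 are called safe

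*Protocol*

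**What the plan says.** The Protocol's pre-procedure bleeding check is in Section 4 (Study Description). Bleeding risk factors are reviewed first, and laboratory testing follows only where one is present: "In patients with any risk factors, their platelet (PLT) count and coagulation status will be tested and controlled by the physician performing TCB". Section 4.1 agrees, saying that the procedure needs no "laboratory tests (except in patients with high risk of bleeding").

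For patients with abnormal results the paragraph continues: "In patients with thrombocytopenia or a prolonged prothrombin time and activated thromboplastin time, preventive measures should be discussed with a hemostasis specialist". The next sentence gives the numeric limits. A platelet count above 50 × 10⁹/L is paired with the statement that "an international normalized ratio (INR) > 1.5 are considered safe", citing references 12 and 13.

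The paragraph then sets timing rules for anticoagulants, including: "In patients using vitamin K antagonists, TCB should be performed at least 5 days after last tablet". It ends: "Patients who are unable to undergo TCB due to hematologic complications will be excluded from the trial".

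**The concern.** The two limits in the sentence carry the same sign, but the two tests run in opposite directions. A low platelet count is the hazard, so calling values above a floor safe is correct. A high INR is the hazard, so the safe side must lie below a ceiling. As printed, the INR limit is a floor.

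This is an operative instruction, not background text, and it is the only numeric limit the Protocol gives for a coagulation test. It applies to patients already selected for bleeding risk, among whom a raised INR is most likely to be found. Bleeding is a real hazard of the procedure: Section 1 reports two bleeding complications resolved by surgery in the centre's earlier series of 190 patients, and Section 4.1.1 requires at least three needle passages. What is at stake is patient safety. The calculation of the sample size and the planned analysis do not depend on this limit.

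**Working it through.** The sentence contains no derived figure to reproduce, so the check is one of direction and consistency.

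**Inputs, all from Section 4 of the Protocol**
- Platelets: safe above 50 × 10⁹/L.
- INR: safe above 1.5, as printed.
- Prolonged prothrombin time, named together with activated thromboplastin time: discuss preventive measures with a hemostasis specialist.
- Vitamin K antagonists: wait at least 5 days after the last tablet.

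**Step 1: what INR measures.** INR is the patient's prothrombin time expressed as a standardised ratio to normal. A normal value is about 1, and the value rises as the prothrombin time lengthens. This is the definition of the test and needs no cited source.

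**Step 2: compare with the preceding sentence.** An INR above 1.5 is a prolonged prothrombin time. One sentence makes that finding a reason for specialist advice; the next calls it safe.

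**Step 3: compare with the vitamin K antagonist rule.** These drugs raise the INR. A wait of at least 5 days after the last tablet makes sense only if a raised INR is to be avoided at biopsy. The printed limit implies the opposite.

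**Step 4: apply the rule in both directions.** The INR values are assumed, for illustration, and platelets are taken to be above their limit.

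| INR | As printed (> 1.5 safe) | Sign reversed (< 1.5 or ≤ 1.5 safe) |
|---|---|---|
| 1.0 | not safe | safe |
| 2.0 | safe | not safe |
| 3.0 | safe | not safe |
| 5.0 | safe | not safe |

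The printed rule gets all four rows the wrong way round and sets no upper bound on INR. The table shows direction only; it does not estimate how many patients are affected.

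**Step 5: look for a correction elsewhere.** INR is mentioned once in the Protocol. No eligibility criterion in Sections 3.1 or 3.2, and nothing in Section 4.1, restates or overrides the limit.

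**The case against.** The strongest reply is that the slip exposes itself. A rule that puts a normal INR outside the safe range cannot be followed by any physician, and Section 4.1 limits the procedure to trained operators. The limit is also not the only barrier. It is paired with the platelet count, so INR alone does not clear a patient. A prolonged clotting time calls for a specialist discussion. The likeliest cause of a raised INR, vitamin K antagonist use, has its own waiting period, and patients who cannot have the biopsy for hematologic reasons are excluded. These points stand, and they lower the chance of harm. They do not remove it: the specialist sentence can be read as requiring both clotting times to be prolonged, and it recommends a discussion without forbidding the biopsy. Nor do they make the sentence right.

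A second reply is that the sign may have been misread when the text was extracted from the PDF. This cannot be fully excluded. However, the less-than sign comes through correctly in the Synopsis, in Sections 3.1 and 3.2 and in the flow chart, although those are short list items and not running prose. Nothing positively suggests a misreading, and an author's repetition of the platelet sign would explain the text equally well. One look at the source file settles it.

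Finally, whether the corrected limit should include 1.5 itself depends on references 12 and 13, which are not available here. Only the direction is established.

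**Conclusion.** The concern holds. The INR limit is reversed as written and conflicts with two other instructions in its own paragraph, and no other text corrects it. It must be fixed because it is a decision limit in a safety instruction.

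Its practical reach is limited and cannot be quantified. It extends to patients who are tested because of a bleeding risk factor and whose INR exceeds 1.5, and the Protocol gives neither count. The conclusion rests on the definition of INR and on the printed sign being the one in the source file. Confidence in the direction of the error is high.

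**What to change.** 1. Check the sign in the source file of Protocol version 2.0.
2. If it reads as quoted, reverse it, so that the safe condition is a platelet count above 50 × 10⁹/L together with an INR below (or at most) 1.5. Take the choice between < and ≤ from references 12 and 13.
3. Issue the corrected sentence and notify every physician who performs TCB in the study.

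The cost is one character in one sentence and a short notice. The design, sample size and analysis do not change.

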4.1. DESCRIPTION OF TCB

Because of the very low rate of complications associated with pelvic TCB, it is considered a low-risk procedure and, as such, can be performed in an outpatient basis. It does not require any special preparation of the patient, laboratory tests (except in patients with high risk of bleeding), fasting, or general anesthesia, and it involves a short procedure time. Anxious, risky patients and those who are unable to tolerate US should be offered conscious sedation or general anesthesia in an inpatient setting. Patients referred for surgical treatment according to clinical staging will undergo TCB just

before main surgery under anesthesia. For the other patients, TCB should be done as soon as possible after US, with a maximum interval of 1 week.

The physician who performs TCB according to US will choose the best suitable approach, such as vaginal/ transrectal or abdominal/percutaneous; in some cases, both routes may be used. If the lesion is accessible by two different approaches (transvaginal and percutaneous), the preferred approach is transvaginal because the needle is easier to control, the needle tip can be continuously monitored easily, the higher resolution of the endovaginal probe, and the gynecologist usually has greater experience of this approach. All biopsies will be performed by physicians with training in performing gynecologic US and TCB.

Antibiotic prophylaxis is recommended after transrectal biopsy if the needle passes through the rectal wall into the peritoneal cavity and in immunocompromised patients [15, 16]. The main principles of clean contaminated procedures must be followed when performing invasive procedures to minimize the risk of infection.

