2.3. Additional endpoints

1. To evaluate which factors affect the primary and secondary endpoint, including:
 - a. tumor origin
 - b. size of the tumor
 - c. presence of ascites
 - d. body mass index (BMI)
 - e. biopsy site
 - f. biopsy approach transvaginal, transrectal vs. transabdominal
 - g. disease status – the first diagnosis, the first and other recurrence or progression
 - h. previous treatment modality – chemotherapy, anti-angiogenic therapy, PARP inhibitor therapy, hormonal therapy, or radiotherapy
2. To evaluate the overall safety of TCB
3. To evaluate the overall accuracy of TCB for complex classification of pelvic and abdominal tumors

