2.4. Definitions of endpoints

The feasibility of TCB will be calculated as the proportion of patients in whom TCB was performed among all patients enrolled in the study.

Adequacy is defined as the proportion of patients in whom an adequate sample was obtained for a particular examination from among those patients who underwent TCB.

Accuracy will only be evaluated in patients in whom an adequate sample was obtained by TCB who underwent surgery with biopsy. Accuracy is defined as the concordance between the examination of samples obtained by TCB and the results of surgery with TCB to the final histopathology. The outcome of the final histopathological examination will be considered the reference standard.

For accuracy and adequacy, the impact of selected variables (e.g., approach, number of biopsies, and target lesion size) will be assessed in a multivariable analysis.

Safety is defined as the rate of complications related to TCB, including events occurring during the procedure, events within 24 hours after the procedure (early events), and events within 30 days of the procedure (late events).

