evaluation form, and details of AEs will be recorded using *the AE evaluation form*. AEs will be prospectively assessed according to the Clavien–Dindo classification (Attachment 1) [19]. AEs will be reported separately according to whether they occurred during the procedure, within 24 hours after the procedure, or within 30 days after the procedure. Furthermore, the patients will be contacted by telephone within 72 hours to enquire about their subjective assessment of the procedure.

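### In patients biopsied just before main surgery, the 24-hour and 30-day safety windows coincide with the operation, so including them can bias the overall early and late complication rates of TCB in either direction

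*Protocol*

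**What the plan says.** Section 4.1 describes two settings. For one group, "Patients referred for surgical treatment according to clinical staging will undergo TCB just" "before main surgery under anesthesia". For everyone else the biopsy is an event of its own: "For the other patients, TCB should be done as soon as possible after US, with a maximum interval of 1 week".

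Safety is an additional endpoint. Section 2.3 states the aim without distinguishing the settings: "To evaluate the overall safety of TCB". Section 2.4 gives the definition: "Safety is defined as the rate of complications related to TCB, including events occurring during the procedure, events within 24 hours after the procedure", followed by a last category, "events within 30 days of the procedure (late events").

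Section 4.1.1 fixes the breakdown by time alone: "AEs will be reported separately according to whether they occurred during the procedure, within 24 hours after the procedure", or within 30 days. Events are graded by Clavien–Dindo. Section 6 follows every participant for 30 days after TCB for any adverse event. The multivariable analysis in section 2.4 names accuracy and adequacy, not safety.

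The protocol does not separate the two settings in the safety analysis, stop counting at the main operation, or say how or by whom relatedness to TCB is judged.

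**The concern.** A patient biopsied under the anesthesia of her main operation spends the next 24 hours, and most or all of the next 30 days, in postoperative recovery. A bleed, an infection or an organ injury in that time has two candidate causes, which may lie at the same site on the same day. Two opposite errors follow:

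- **Upward.** A surgical complication is counted as a TCB complication.
- **Downward.** A TCB complication is dealt with during the operation and not recognised as such, while the patient still counts in the denominator.

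Section 7 expects the study to confirm the safety of TCB, and section 4.1 presents TCB as a low-risk procedure that can be done on an outpatient basis. The rate that bears on that statement is the rate after a biopsy not followed at once by an operation. An overall early or late rate mixes that quantity with one that depends on how many patients went straight to surgery and how their events were attributed.

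**Working it through.** **1. The windows by setting**

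| Window (section 2.4) | Stand-alone TCB | TCB just before main surgery |
|---|---|---|
| During the procedure | TCB only | TCB only, as surgery has not begun |
| Within 24 hours | TCB only, unless surgery follows | Includes the operation and its immediate recovery |
| Within 30 days | TCB only, unless surgery follows | Includes the operation and recovery |

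The problem is confined to the lower two cells of the right-hand column and to any overall rate that includes them.

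**2. Whether the protocol's own tools separate the causes**

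- The words limiting safety to complications related to TCB show that attribution is intended, but no rule or assessor is given.
- Clavien–Dindo grades severity, not cause.
- The ultrasound check at the end of the biopsy (section 4.1.1) does observe TCB alone, but in this group that period ends when surgery begins.
- The telephone call within 72 hours falls after the operation.

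**3. Size**

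The protocol states no target rate, expected rate or sample size for safety, so there is no planned figure to reproduce. What follows is an illustration.

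Inputs:
- *t* = 2/190 = 1.05%, from the site's retrospective series in section 1 (exact 95% CI 0.13% to 3.75%).
- *f* = share biopsied just before surgery. Not in the protocol; assumed 20% to 40%.
- *s* = proportion of that group with a surgical event counted as a TCB event. Not in the protocol; assumed 2% to 10%, and added to *t*.

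Surgical events counted: overall rate = (1 − *f*)·*t* + *f*·(*t* + *s*) = *t* + *f*·*s*.

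| *f* | *s* | Overall rate |
|---|---|---|
| 20% | 2% | 1.05% + 0.40% = 1.45% |
| 20% | 10% | 1.05% + 2.00% = 3.05% |
| 40% | 2% | 1.05% + 0.80% = 1.85% |
| 40% | 10% | 1.05% + 4.00% = 5.05% |

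All TCB events in the pre-surgical group masked: overall rate = (1 − *f*)·*t*.

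- *f* = 20%: 0.80 × 1.05% = 0.84%
- *f* = 40%: 0.60 × 1.05% = 0.63%

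**4. Precision left after a split**

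With 250 patients, a 20% to 40% pre-surgical share leaves 200 to 150 stand-alone biopsies. At about 1% the expected number of events is 2 or 3. Exact 95% upper limits are 3.5% for 3/250, 3.6% for 2/200 and 4.7% for 2/150.

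**5. Why the split must use the planned setting**

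Both complications in the earlier series were bleeds resolved by surgery. A safety set restricted to patients with no surgery inside the window would drop such patients. Applied to those figures, 2/190 would become 0/188, with an exact upper limit of 1.9%. That rule selects on an outcome of the biopsy and removes its most serious complications.

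**The case against.** The strongest defence is that section 2.4 counts only complications related to TCB, that section 4.1.1 requires an ultrasound check for bleeding before the procedure ends, and that the TCB and adverse event forms must be completed. Some basis for attribution therefore exists, and it is not established that a biopsy bleed would go unrecorded. This stands for events seen before surgery starts. It does not help for later events, where no written rule separates the biopsy from the operation.

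A reader might infer that the whole safety endpoint is uninterpretable. The documents do not support that. The three windows are reported separately, the intra-procedural rate is clean in both settings, and stand-alone patients are unaffected.

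A reader might also take pooling as stated. It is inferred from a single overall rate and a breakdown by time only. A statistical analysis plan, not at hand, could add a split. The definition and the breakdown are nevertheless fixed in the protocol and do not suit one of its two settings.

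The numbers are open to challenge. Neither *f* nor *s* has a source in the protocol. Section 1 says TCB is mostly used where complete primary cytoreduction is not feasible, and section 3.2 excludes early-stage disease, so the pre-surgical share may be lower than assumed. The earlier series also included patients indicated for surgery, so 1.05% is not a pure stand-alone rate, and the protocol does not say in which window its two bleeds fell. The masked results lie well inside that rate's own confidence interval.

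**Conclusion.** The point holds for the 24-hour and 30-day windows in patients biopsied just before main surgery, and through them for the overall early and late rates. Events there cannot be reliably attributed to TCB, and the bias can go either way.

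Under the assumed 20–40% share, a rate of 1.05% would appear as 1.5–5.1% with surgical events counted in 2–10% of that group, or as 0.6–0.8% with every TCB event in it masked. These ranges show direction and order of size. They are not predictions, and the upper end requires surgical events to be counted despite the limit to TCB-related complications.

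Safety is an additional endpoint without a hypothesis or target, and the primary adequacy endpoint is untouched. The change is still worth making, because confirming safety is among the study's stated expectations.

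**What to change.** Amend section 2.4, and align the reporting sentence in section 4.1.1, as follows:

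1. Split the safety analysis by the setting planned at the time of biopsy: stand-alone, or just before main surgery.
2. Base the main 24-hour and 30-day rates, with exact 95% confidence intervals, on patients planned for stand-alone TCB.
3. Report the pre-surgical group separately, only for events from the biopsy to the start of the main surgery.
4. In stand-alone patients who later have planned surgery within 30 days, end the counting of TCB events at the start of that surgery.
5. Keep surgery done for a TCB complication as a TCB event. Do not exclude or censor these patients.

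No clinical procedure changes. The cost is a smaller denominator and a somewhat wider interval (upper limit about 3.6% to 4.7% instead of 3.5% in the illustration). The planned setting and the date of any surgery must be available in the study forms. The protocol names the forms but does not show their fields, so this should be checked.
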